### **3.2. Study Duration**

Subjects will be screened within 35 days prior to administration of the investigational product to confirm that they meet the subject eligibility criteria for the study. At the Day 1 clinic visit, eligibility criteria will be confirmed. Subjects will begin dosing on Day 1. Subjects will be required to return to the clinic (eg, study site) for PK/PD sample collection on Day 2 and Day 4. Subjects will then be required to attend weekly clinic visits on Day 8, Day 15, Day 22, and Day 29. For subjects with once weekly (QW) dosing frequency, investigational product will be administered at these visits as well.

Following Day 29, provided that safety was confirmed for the cohort and no stopping criteria were met, all subjects in each cohort will return to the clinic for PK/PD sample collection on Day 30 and Day 33. Subjects in the SC cohorts will receive treatment on Day 36, Day 43, Day 50, Day 57, Day 64, Day 71, Day 78, follow-up on Day 85, and end-of-study procedures on Day 113. For the Day 36, 43, 50, 64, 71 and 78 SC treatments, in countries where approved by respective competent authorities and at sites where it is approved by the respective IRB/EC, SC treatment with investigational product may be administered by investigator site personnel in a home care or ambulatory clinic setting. Subjects in the IV cohort will receive treatment on Day 57, follow-up on Day 85, and end-of-study procedures on Day 113.

Subjects with positive ADA or NAb results may be requested to return for additional follow-up visits after Day 113.

Subjects who experience a treatment-related adverse event (including lab abnormalities) at any time point will continue to be followed through resolution or stabilization of the event as agreed upon by the investigator and Sponsor.

The maximum total duration of the study for a single subject, from initial screening to final follow-up, will be approximately 5 months.

During the study data will be reviewed on an ongoing basis to determine if PF-06741086 is safe and tolerated. Dosing of subjects in any cohort may be stopped if the B7841002 protocol-specified stopping criteria are met ([Section 3.3](#)). If available data are permissive for dose progression, subjects will be recruited into the next cohort in the study and dosed at the next dose level of PF-06741086.

### 3.3. Dose Escalation and Stopping Rules

Dose escalation stopping rules will be used to determine whether the maximum tolerated dose has been attained.

Dose escalation will not occur if 2 or more dose-limiting toxicities are met within a dosing cohort of 6 subjects. Dose escalation may occur if  $\leq 1$  dose limiting toxicity is observed within a dosing cohort of 6 subjects. Dose limiting toxicities are defined as:

- Treatment emergent laboratory abnormality as specified in [Appendix 2](#);
- Treatment emergent vital sign abnormality as specified in [Appendix 2](#);
- Treatment emergent ECG abnormality as specified in [Appendix 2](#);
- Treatment emergent severe or  $\geq$  Grade 3 adverse event, as graded by the NIAID DMID criteria for severity unless incontrovertibly due to extraneous causes.

Additional rules governing dose escalation are as follows:

- Dosing at the current dose level (or higher dose levels) will be suspended for any treatment emergent thrombotic event (see [Appendix 1](#) for qualifying AEs) in a subject receiving PF-06741086 to permit characterization of the respective event and communication to regulatory agencies where required. Vessel occlusion related to the insertion or presence of a central venous catheter may be excluded from this criterion after review of the AE with the respective investigator to assess causality and/or clinical significance.
- All treatment emergent adverse events, regardless of system organ class, severity/grade, causality, and/or attribution to treatment with PF-06741086 are assessed and it is determined by the Sponsor that the limit of safety and/or tolerability has been reached.
- Dose escalation will be paused for any treatment emergent serious adverse event (SAE) that occurs in a subject receiving PF-06741086 until causality is fully assessed by the Sponsor. Dose escalation will cease if the SAE is determined to be either drug-related or unknown, and may resume if the SAE is determined to be not drug-related by the Sponsor.
- If, based on the observed data, the group geometric mean  $C_{\max}$  or area under the curve ( $AUC_{168}$ ) (based on total concentration with either the first dose or at steady-state) of the next planned regimen is projected to exceed the exposure limits ( $AUC_{168}$  of 1,940,000  $\mu\text{g}\cdot\text{h}/\text{mL}$  and  $C_{\max}$  of 27,800  $\mu\text{g}/\text{mL}$ ), that dose will not be explored. Modified doses may be explored if they are not expected to exceed these PK stopping criteria.

In addition, tolerability criteria for dose escalation are:

- For SC cohorts: no more than 2 subjects in a dosing cohort of 6 subjects experience at least moderate severity injection site reactions.
- For IV cohorts: no more than 2 subjects in a dosing cohort of 6 subjects experience at least moderate severity infusion/injection site reactions.

Progression to a higher dose level or regimen not assessed as safe and well tolerated in a previous cohort will follow the Sponsor's review of the available safety, PK, PD, and bleed rate data through study Day 29 (at a minimum) in 100% (ie, 6 of 6) of subjects in the current cohort. Accumulated safety, PK, PD, bleed rate and immunogenicity data from previous cohorts will also be reviewed. Progression to the next cohort will occur if the current dose level is well tolerated and after satisfactory review of these data.

For doses with projected  $C_{max}$ /AUC levels not previously achieved in humans, sequential dosing will be implemented for the first 3 subjects at the respective dose level. Following initial dosing for each of the first 3 subjects, available safety and laboratory data through 72 hours post-dose will be monitored. Subsequent dosing for the cohort shall not commence until satisfactory review of these data is complete.

If at any time during cohort enrollment data suggest that stopping rules may have been met then dosing will be suspended. A formal review of available data by the Sponsor study team will determine whether stopping rule criteria have been met.

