### 1.3.2. Study Rationale

The clinical investigation of PF-06741086 will continue with study B7841002, an open-label, Phase 1b/2, multiple ascending dose (MAD) study in severe hemophilia A or B subjects, including subjects with inhibitors to factor VIII or factor IX. The clinical risk/benefit profile for this population is considered appropriate for the evaluation of safety, tolerability, PK, PD, and efficacy of multiple doses of PF-06741086. Frequency of bleeding episodes (of study subjects during treatment with PF-06741086) will be compared against the frequency of bleeding episodes in an external control group as a measure of therapeutic efficacy.

The primary objective of study B7841002 is to evaluate the safety and tolerability of multiple ascending doses of PF-06741086 administered by the SC or IV route. Secondary objectives include evaluating the PK and PD properties of PF-06741086, as well as assessing clinical efficacy based on the frequency of bleeding episodes. Selection of the PD endpoints and sampling schedule are based on results from non-clinical studies and the Phase 1 FIH study results. They will reflect either target binding by PF-06741086 (ie, TFPI level) or downstream pharmacologic effects of TFPI inhibition (ie, dPT, TGA, PF1+2 and D-dimer). Thrombosis is a potential risk for inhibition of TFPI, and PF-06741086 is expected to significantly inhibit TFPI, particularly at the highest dose levels. To minimize this risk, hemophilia patients with a known history of thrombotic, ischemic or coronary artery disease, or known pro-thrombotic conditions (eg, Protein C deficiency) will be excluded from this study. Safety monitoring will include laboratory parameters that may be modulated due to coagulopathy (eg, [PT]/INR, aPTT, fibrinogen, ATIII and platelet counts) and parameters to screen for possible thrombotic events (eg, cardiac troponin I). Laboratory endpoints to detect excessive modulation of the coagulation pathway will be monitored during the period of peak drug exposure, until at least 28 days have passed since the final administration.

Potential risks for treatment with PF-06741086 are thrombi or emboli. Depending on location and severity, thrombi or emboli may be life threatening or fatal. An additional potential risk for treatment with PF-06741086 is ADA-induced hypersensitivity.

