### 6.2.1. Day 1 Visit

**Prior to dosing** on Day 1 the following procedures will be completed:

- Assess baseline symptoms/AEs including interval since Screening;
- Review changes in subject's concomitant treatment information since Screening;
- Review use of Factor VIII or Factor IX replacement therapy, or rFVIIa bypass agent therapy to ensure subject meets washout criteria prior to Day 1;
- Review changes in the subject's medical history including medication history since Screening;
- Collect information on new bleeding episodes;
- Review Inclusion and Exclusion criteria;
- Conduct a limited physical examination at the discretion of the investigator, if clinically indicated, to assess changes since Screening of any ongoing symptoms;
- Collect weight;
- Confirm proper contraception is being used;

- Obtain pulse rate, respiratory rate, oral temperature, and supine blood pressure;
- Collect triplicate 12-lead ECG.
- Collect blood and urine specimens for the following for shipment to the study central laboratory:
  - Urinalysis;
  - Serum chemistry;
  - Hematology with differential panel;
  - Factor VIII and Factor IX activity;
  - Banked biospecimens;
  - TFPI level;
  - PT/INR;
  - aPTT;
  - Fibrinogen;
  - ATIII;
  - TGA;
  - PF1+2;
  - D-dimer;
  - dPT;
  - Cardiac Troponin I;
  - PK blood sampling;
  - Immunogenicity (ADA, NAb);
-  Treatment assignment any time prior to dosing once subject has met all eligibility criteria;

- After all pre-dose procedures have been completed, administer the investigational product (see [STUDY TREATMENTS](#) and [Administration](#) Sections).

**After dosing**, the following procedures will be completed:

- **IV cohorts only:** Collect blood samples from the arm not used for IV IP administration immediately following completion of the IV line flush after completion of the IV infusion. These blood samples are for shipment to the study central laboratory:
  - TFPI level;
  - TGA;
  - PF1+2;
  - D-dimer;
  - dPT;
  - PK blood sampling.
- Monitor infusion/injection site reactions.
- Assess symptoms by spontaneous reporting of adverse events and by asking the subjects to respond to a non-leading question such as “How do you feel?”
- Issue subject diary and provide training with respect to completing the diary including timing and nature of information to be entered.

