#### **6.2.2. Day 2 (-6 hours/+1 day) and Day 4 (-6 hours/+1 day) PK/PD Blood Draws**

The following procedures will be completed 24 (-6/+24) and 72 (-6/+24) hours following investigational product administration on Day 1:

- Obtain information regarding the use of concomitant treatment and the occurrence of adverse events;
- Collect information on new bleeding episodes;
- Monitor infusion/injection site reactions;
- Assess symptoms by spontaneous reporting of adverse events and by asking the subjects to respond to a non-leading question such as “How do you feel?”
- Collect blood samples for the following for shipment to the study central laboratory:

- TFPI level;
- TGA;
- PF1+2;
- D-dimer;
- dPT;
- PK blood sampling.

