### **6.2.3. Day 8 ( $\pm 1$ day), Day 15 ( $\pm 2$ days), Day 22 ( $\pm 2$ days) and Day 29 ( $\pm 2$ days) Visits**

The following procedures will be completed:

- Obtain information regarding the use of concomitant treatment and the occurrence of adverse events;
- Collect information on new bleeding episodes;
- Conduct a limited physical examination at the discretion of the investigator, if clinically indicated, to assess changes from baseline/previous visits of any ongoing symptoms;
- Collect weight (**Day 29 only**);
- Confirm proper contraception is being used;
- Collect the subject's diary and review with the subject/caregiver, including information about study compliance, bleeding assessments (including site and traumatic/spontaneous) and injection site reactions. Dispense new subject diary;
- Collect single 12-lead ECG. If ECG is abnormal, collect triplicate ECG;
- Obtain pulse rate, respiratory rate, oral temperature, and supine blood pressure;
- Collect urine for urinalysis for shipment to the study central laboratory.
- Collect blood samples for the following for shipment to the study central laboratory:
  - Serum chemistry;
  - Hematology (with differential panel on Day 29 only);
  - TFPI level;

- PT/INR;
- aPTT;
- Fibrinogen;
- ATIII;
- TGA;
- PF1+2;
- D-dimer;
- dPT;
- Cardiac Troponin I;
- PK blood sampling;
- Immunogenicity (ADA, NAb) (**Days 15 and 29 only**);

**C**

- **Cohorts with SC administration:** After all pre-dose procedures have been completed, administer the investigational product (see [STUDY TREATMENTS](#) and [Administration](#) Sections) (**Days 8, 15, 22 and 29**).
- **Cohorts with IV administration:** After all pre-dose procedures have been completed, administer the investigational product (see [STUDY TREATMENTS](#) and [Administration](#) Sections) (**Day 29 only**)

**After dosing**, the following procedures will be completed:

- **IV cohorts only (Day 29 only):** Collect blood samples from the arm not used for IV IP administration immediately following completion of the IV line flush after completion of the IV infusion. These blood samples are for shipment to the study central laboratory;
- Monitor infusion/injection site reactions;
- Assess symptoms by spontaneous reporting of adverse events and by asking the subjects to respond to a non-leading question such as “How do you feel?”

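### At 1000 mg IV, the binding 72-hour review of the first three subjects has no scheduled post-dose value for any of the 14 routinely measured Appendix 2 laboratory, vital-sign and ECG items

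*Protocol*

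**What the plan says.** Protocol Section 3.3 calls for sequential dosing of the first three subjects at any dose whose projected Cmax or AUC has not been reached in humans. After each of the three, "available safety and laboratory data through 72 hours post-dose will be monitored". The review is binding: "Subsequent dosing for the cohort shall not commence until satisfactory review of these data is complete".

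The visit sections determine what that review can contain.

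- **Day 1 (Section 6.2.1).** Vital signs, triplicate ECG, chemistry, hematology, PT/INR, aPTT, fibrinogen, ATIII and troponin all sit in the pre-dose block, which opens with the statement that before dosing "on Day 1 the following procedures will be completed". Blood drawn after an IV infusion is for TFPI, TGA, PF1+2, D-dimer, dPT and PK only.
- **Days 2 and 4 (Section 6.2.2).** "The following procedures will be completed 24 (-6/+24) and 72 (-6/+24) hours following investigational product administration on Day 1". These are adverse events, concomitant treatment, bleeds, site reactions and the same PK and pharmacodynamic panel.
- **Day 8 ±1 day (Section 6.2.3).** This visit has the first post-dose vital signs, ECG and safety panel.

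Appendix 2 lists the laboratory, vital-sign and ECG findings that count as dose-limiting toxicities. Section 3.3 adds severe or Grade 3 adverse events, "graded by the NIAID DMID criteria for severity unless incontrovertibly due to extraneous causes". Section 1.3.2 names PT/INR, aPTT, fibrinogen, ATIII and platelets as coagulation safety parameters and says: "Laboratory endpoints to detect excessive modulation of the coagulation pathway will be monitored during the period of peak drug exposure".

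**The concern.** The sequential step exists to catch a problem in one subject before the next is exposed. For laboratory, vital-sign and ECG changes, the protocol's objective definition of a problem is Appendix 2. Yet the schedule supplies none of those values in the review window.

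The review could therefore be satisfactory on paper while an asymptomatic change in platelets, fibrinogen, PT, troponin or QTcF after a first 1000 mg infusion went unmeasured. Section 7.8 requires an immediate repeat visit for low platelets, fibrinogen or hemoglobin, or a raised PT/INR, but no scheduled sample can trigger it before Day 8. The study has no data monitoring committee (Section 9.8).

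**Working it through.** **1. Count the items.** Appendix 2 has 17 rows, taking blood pressure as one: hematology 3, chemistry 5, coagulation and troponin 3, vital signs 3, ECG 3. Direct bilirubin, indirect bilirubin and creatine kinase appear in Table 5 only as liver-injury follow-up tests. 17 − 3 = 14 routine items.

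**2. Check the schedule against the blood-volume table.** Tables 1 and 2 place chemistry and hematology on Days 1, 8, 15, 22, 29, 57 and 85, which is 7 draws each. Troponin falls on Days 1, 8, 15, 22 and 29, which is 5. Table 7 gives 7, 7 and 5, so no draw is left for Day 2 or Day 4.

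**3. Items with a post-dose value, by hours after the first dose.**

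| Window | Items of 14 |
|---|---|
| to 72 h | 0 |
| to 96 h (Day 4 plus its window) | 0 |
| first value, nominal (8 − 1) × 24 | 168 h |
| first value, earliest (168 − 24) | 144 h |

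Splitting blood pressure into two items leaves the count at zero. Section 7.1.6 mentions triplicate ECGs at each nominal time point on Day 1, but Section 6.2.1 lists only a pre-dose one and SAP Section 3.1.4 takes baseline from pre-dose triplicates.

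**4. How new is the exposure?** Table 4 gives predictions for 1000 mg IV and 450 mg SC; Table 3 gives observed values for 440 mg IV.

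- Peak: 313/152.8 = 2.05 times the highest observed. For the first infusion, subtracting the whole predicted trough: (313 − 8.98)/152.8 = 1.99.
- AUC168 against the highest observed AUC: 26.6/14.38 = 1.85. First infusion: 26.6 − 8.98 × 168/1000 = 25.09, and 25.09/14.38 = 1.74.
- AUC168 against predicted 450 mg SC steady state, if that cohort is completed first: 26.6/21.5 = 1.24. First infusion: 25.09/21.5 = 1.17.
- 450 mg SC is not part of this point. Its predicted peak is 134/152.8 = 0.88 of the observed maximum. It is new only on steady-state AUC (21.5/14.38 = 1.50), where weekly panels to Day 29 already apply.

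**5. Concentration at each visit (illustrative only).** Assume a one-phase decline with k solving Cmax × (1 − e^(−168k))/k = AUC168. At steady state the half-life is 74.5 h, so k = 0.0093 per hour.

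- 24 h: 313 × e^(−0.0093 × 24) = 250 µg/mL.
- Day 4 window: 169 at 66 h and 128 at 96 h.
- Time above 152.8: ln(313/152.8)/0.0093 = 77 h.

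The variants start from 313 or 304 µg/mL and may put 10–30% of the peak in a fast phase with a half-life of 12 or 24 h. Across them, time above 152.8 is 64–77 h, the Day 4 window spans about 119–169 µg/mL and 168 h gives 59–95 µg/mL. The lowest 24 h value is 304 × [0.3 × 2^(−24/12) + 0.7 × 2^(−24/128.5)] = 210 µg/mL. So Day 2 samples well above the prior maximum, and Day 4 largely at or below it.

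The model is weak. At 672 h the one-phase curve gives 313 × e^(−0.0093 × 672) = 0.6 µg/mL, against a Table 4 trough of 8.98.

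**6. Shortest spacing the rule allows.** At 72 h per subject, doses fall at 0, 72, 144 and 216 h. Day 8 panels for subjects 1, 2 and 3 fall at 144–192, 216–264 and 288–336 h. Subjects 2 and 3 could be dosed before any post-dose panel result must exist. This is a minimum, with no allowance for recruitment or review time.

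**The case against.** The strongest reply is that Section 3.3 asks for available data and does not cite Appendix 2 in the sequential-dosing rule. Laboratory data are scheduled: D-dimer, PF1+2, dPT, TGA, TFPI and PK at end of infusion, 24 h and 72 h, with adverse events and site reactions. These markers follow the mechanism of concern. Unscheduled labs are allowed (Section 7.1.1), and there is a further safeguard: "If at any time during cohort enrollment data suggest that stopping rules may have been met then dosing will be suspended".

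Much of this stands. A reader might infer that the review is empty or that Section 3.3 contradicts the schedule; neither is so. But the markers have no Appendix 2 limits, unscheduled labs answer a concern someone has already perceived, and the suspension rule needs an event or a result to act on.

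A reader might also infer that the drug's effect has passed by Day 8. The documents point the other way. The modelled EC90 values in Section 1.3.3.1 are 0.765, 2.84 and 35.4 µg/mL, and the illustrative Day 8 range of 59–95 exceeds all three. On those models a higher peak adds at most 10% of maximal effect. They describe pharmacodynamic markers, however, and not platelets, troponin or QTcF.

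Finally, progression requires review through Day 29 in all six subjects of the current cohort, plus earlier cohorts. In the planned order that includes weekly panels at 450 mg SC. This lowers the AUC novelty to about 1.24 times but leaves the peak new.

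**Conclusion.** The point holds and should be fixed before the first 1000 mg IV subject is dosed. For that subject and the next two, 0 of 14 routine Appendix 2 laboratory, vital-sign and ECG items are scheduled before Day 8 (±1 day), at a predicted peak 2.05 times the highest seen in humans. The count comes straight from the schedule and needs no assumption beyond treating the three follow-up chemistry tests as non-routine. The exposure ratios rest on Table 4 predictions. The 64–77 h and dose-spacing figures are illustrations and carry no weight in the conclusion.

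A reader might take this as a sign that subjects will be harmed. The documents do not support that. Predicted exposure is 27,800/313 = 89-fold below the Cmax limit and 1,940,000/26,600 = 73-fold below the AUC168 limit. Single doses up to 440 mg IV in healthy subjects produced no serious or severe events, and Section 1.3.4 expects lower thrombotic risk in hemophilia. The defect is that a binding check lacks the measurements that would make it informative.

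**What to change.** For the first three subjects at any regimen whose first-dose exposure is new:

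1. Run PT/INR, aPTT and fibrinogen on the combined citrate tube already drawn on Days 2 and 4 (Table 7 describes one tube shared with D-dimer and PF1+2), once the central laboratory confirms there is enough plasma. Record vital signs after the infusion and on Days 2 and 4.
2. Add hematology (3 mL), chemistry (5 mL), troponin (3 mL) and a single ECG on Day 2, nearer the peak, with the option to repeat on Day 4. Day 4 alone would largely miss the new exposure range.
3. State in Section 3.3 that the review covers data through the Day 4 visit and is complete only when these results are in.

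All 14 items would then have a value before the next subject is dosed.

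**Cost.** An amendment to Section 3.3, Tables 1 and 7 (and Table 6 if a SC regimen qualifies), and Sections 6.2.1, 6.2.2 and 7.7. No extra visit is needed. Blood: 5 + 3 + 3 = 11 mL if drawn once, 22 mL if repeated. The Table 7 whole-study total rises from 433.2 to 444.2 or 455.2 mL, under the cap of 550 mL per 30 days. Assay and ECG costs are small. The main downside is a short wait for central-laboratory results at each step; the documents give no turnaround time.

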### **Dose Modifications**

Any subject who experiences a dose limiting toxicity (per [Appendix 2](#)) will be discontinued from treatment with the investigational product and will be followed for adverse event monitoring until resolution of the respective toxicity and elimination of study drug or the end of the study (Day 113) and resolution or stabilization of the respective toxicity, whichever occurs first. In addition, subjects who have not experienced dose limiting toxicities but are currently receiving a dose that met the dose limiting toxicities criteria for termination of dose escalation as defined in [Section 3.3](#) will be removed from the current dose level and dropped to the next lowest exposure level.

Subjects who have not experienced a dose-limiting toxicity may also require dose modifications. Criteria for modifications of dosing in an individual subject are as follows:

- Moderate severity infusion/injection site reactions at more than 2 consecutive visits (eg, Day 22, Day 29, and Day 36);
- Treatment emergent adverse event(s) that increases in severity/grade, without resolution, (eg, Mild to Moderate and continuing) after repeat administration of PF-06741086;

- Treatment emergent adverse event(s) of any severity with more than 2 occurrences following repeat administration of PF-06741086.

Any subject who meets the above criteria during treatment with PF-06741086 will be removed from the current dose level and dropped to the next lowest exposure level, unless the event(s) are incontrovertibly due to extraneous causes or are incontrovertibly complications of hemophilia (see [Section 8.6](#) for qualifying events).

